5.5.1. Hyperlipidemia

In the lorlatinib Phase 1 Study B7461001, hypercholesterolemia was the most common AE reported. Elevations in lipids usually begin in the first few cycles and, if statins are not introduced, can rise to Grade 3 levels by the next treatment cycle. Therefore, the suggested management is to begin a statin for Grade 1 elevations in either cholesterol or triglycerides and to increase the statin dose if adequate control is not obtained, as outlined in [Table 2](#).

Members of the statin class of agents are differentially sensitive to CYP3A4, and **caution should be exercised when selecting statin for management of elevated lipid levels**.

Pitavastatin and rosuvastatin can be used during lorlatinib treatment without dose adjustment since there is no CYP3A4 involvement in their elimination. Pravastatin, fluvastatin and atorvastatin should be used with caution during lorlatinib treatment, and a dose adjustment of these statins may be necessary (**increasing dose may be considered**). Lovastatin and simvastatin are not recommended for use during lorlatinib treatment.

5.5.2. PR Interval Prolongation

Analysis of ECG data from ongoing and completed human studies with lorlatinib has identified a subset of subjects who exhibited ECG evidence of PR interval prolongation. The ECG changes appear limited to the PR interval with no impact on QRS or QT intervals. This impact on the PR interval is supported by preclinical animal studies as described in the current lorlatinib IB.

Guidance for management of PR interval prolongation is provided in [Table 3](#) below and examples of drug with potential PR interval prolongation effect can be found in [Appendix 5](#).

Table 3. PR Interval Prolongation Management

Toxicity	No symptomatic	Symptomatic
1 st -Degree Heart Block (PR interval >200 msec)	No dose hold or reduction needed. Assess concomitant medications and electrolyte imbalance that may prolong PR interval. Monitor ECG/symptoms potentially related to AV block closely	Withhold dose. Assess concomitant medications and electrolyte imbalance that may prolong PR interval. Monitor ECG/symptoms potentially related to AV block closely. If symptoms resolve, resume at same dose or at 1 reduced dose level
2 nd -Degree Heart Block	Withhold dose. Assess concomitant medications and electrolyte imbalance that may prolong PR interval. Monitor ECG/symptoms potentially related to AV block closely. If subsequent ECG does not show second degree block, resume at same dose or 1 reduced dose level	Withhold dose. Assess concomitant medications and electrolyte imbalance that may prolong PR interval. Refer for cardiac observation and monitoring. Consider pacemaker placement if symptomatic AV block persists. If symptoms and the second degree block resolve or if subjects revert to asymptomatic first degree AV block, resume at 1 reduced dose level
Complete Heart Block	Withhold dose. Assess concomitant medications and electrolyte imbalance that may prolong PR interval. Refer for cardiac observation and monitoring. Temporary pacemaker placement may be indicated for severe symptoms associated with AV block. If AV block does not resolve, placement of a permanent pacemaker may be considered. If pacemaker placed, may resume at full dose. If no pacemaker placed, resume at 1 reduced dose level only when symptoms resolve AND PR interval is less than 200 msec.	

5.5.3. Pneumonitis/Pneumonia

Investigators must evaluate thoroughly subjects who demonstrate potential signs/symptoms of pneumonitis/pneumonia. If a subject has a potential diagnosis of pneumonitis or drug-related lung injury, then the following evaluations/procedures should be considered to confirm or exclude the diagnosis of pneumonitis during this period in the absence of disease progression, other pulmonary disease, infection, or radiation effects:

- A sputum gram stain and culture (induced sputum if needed) bacterial, viral, fungal, protozoal, and mycobacteria.
- Blood culture should be performed in febrile subjects. Consider appropriate serologies (mycoplasma, legionella, cytomegalovirus, other viruses, etc).
- Thoracentesis if pleural fluid is present (culture, microbiology, cytology).

- Bronchoscopy with bronchoalveolar lavage if appropriate. The bronchoalveolar lavage fluid should be sent for culture, microbiology, and cytology (same pathogens as above).
- Lung biopsy (eg, open or thorascopic preferable, bronchoscopy with transbronchial biopsy) if appropriate.
- A plasma sample for BNP (B-type natriuretic peptide) to evaluate for evidence of congestive heart failure.
- For *Asian countries based subjects*, a blood sample for β -D glucan to evaluate for the presence of fungal pneumonia (eg, *Pneumocystis jirovecii*).

If clinically appropriate, high-dose corticosteroid treatment should be initiated. Should the event be fatal an autopsy is highly recommended to confirm/exclude the diagnosis.

5.6. Management of Overdose

An overdose is defined as any dose of lorlatinib >100 mg QD. Any overdose must be recorded in the study drug section of the CRF. If an extra dose is taken during a day, the next dose should not be taken.

For monitoring purposes, any case of overdose, whether or not associated with an AE (serious or not), must be reported to the sponsor (see [Section 8.2.1](#)).

Investigators should use their clinical judgment and treat potential cases of overdose with the appropriate general supportive measures.

5.7. Investigational Product Storage

The investigator or an approved representative, eg, pharmacist, will ensure that all investigational products are stored in a secured area with controlled access under required storage conditions and in accordance with applicable regulatory requirements.

Investigational products should be stored in their original containers and in accordance with the labels. Any storage conditions stated in the SRSD will be superseded by the storage conditions stated on the product label.

Site systems must be capable of measuring and documenting (for example, via a log), at a minimum, daily minimum and maximum temperatures for all site storage locations (as applicable, including frozen, refrigerated, and/or room-temperature products). This should be captured from the time of investigational product receipt throughout the study. Even for continuous-monitoring systems, a log or site procedure that ensures active evaluation for excursions should be available. The intent is to ensure that the minimum and maximum temperature is checked each business day to confirm that no excursion occurred since the last evaluation and to provide the site with the capability to store or view the minimum/maximum temperature for all non-working days upon return to normal operations. The operation of the

temperature monitoring device and storage unit (for example, refrigerator), as applicable, should be regularly inspected to ensure they are maintained in working order.

Any excursions from the product label storage conditions should be reported to Pfizer upon discovery. The site should actively pursue options for returning the product to the storage conditions described in the labeling, as soon as possible. Deviations from the storage requirements, including any actions taken, must be documented and reported to Pfizer.

Once an excursion is identified, the investigational product must be quarantined and not used until Pfizer provides permission to use the investigational product. It will not be considered a protocol deviation if Pfizer approves the use of the investigational product after the temperature excursion. Use of the investigational product prior to Pfizer approval will be considered a protocol deviation. Specific details regarding information the site should report for each excursion will be provided to the site.

Site staff will instruct subjects on the proper storage requirements for take home investigational products.

5.8. Investigational Product Accountability

The investigator site must maintain adequate records documenting the receipt, use, loss, or other disposition of the investigational product supplies. All investigational products will be accounted for using a drug accountability form/record.

All bottles of study drug must be returned to the investigator by the subject at the end of each cycle and at the end of the study. The sponsor will provide instructions as to the process for drug accountability in the monitoring plan.

5.8.1. Destruction of Investigational Product Supplies

The sponsor or designee will provide guidance on the destruction of unused investigational product (eg, at the site). If destruction is authorized to take place at the investigator site, the investigator must ensure that the materials are destroyed in compliance with applicable environmental regulations, institutional policy, and any special instructions provided by Pfizer, and all destruction must be adequately documented.

5.9. Concomitant Treatment(s)

Concomitant treatment considered necessary for the subject's well-being may be given at the discretion of the treating physician.

Concomitant medications and treatments will be recorded from 28 days prior to the start of study treatment and up to 28 days after the last dose of study treatment. All concomitant medications should be recorded in the CRF including supportive care drugs (eg, antiemetic treatment and prophylaxis), and the drugs used to treat adverse events or chronic diseases, and non-drug supportive interventions (eg, transfusions).

Medications intended solely for supportive care (eg, antiemetics, analgesics, megestrol acetate for anorexia, bisphosphonates or receptor activator of nuclear factor kappa-B (RANK)-ligands for metastatic bone disease or osteoporosis) are allowed. In case the patient is already on treatment with RANK-ligands (like denosumab) before study entry, the therapy should be at a stable dose prior to randomization.

There are no prohibited therapies during the Post-Treatment Follow-Up Phase.

5.9.1. Inhibitors and Inducers of CYP Enzymes

The list of food and drugs to be avoided provided below may not be fully exhaustive. Consult the sponsor when in doubt whether a food or a drug falls into any of the categories below.

The in vitro studies have demonstrated that CYP3A, and UGT1A4 are primarily involved in the metabolism of lorlatinib, with additional minor contributions from CYP2C19 and CYP2C8. Inhibition or induction of the above enzymes may result in potential alteration of lorlatinib systemic exposure.

Initial in vitro assessment for inhibition and induction drug-drug interaction potential indicated that lorlatinib is a time-dependent inhibitor of CYP 3A and also an inducer of CYP3A and CYP2B6. At substantially higher concentrations than those observed clinically, lorlatinib also inhibited CYP2C9 in in vitro studies.

To protect subject safety, the following cautions are provided:

- Lorlatinib metabolism may be inhibited by strong CYP3A inhibitors leading to a potential increase in lorlatinib toxicities. Coadministration of strong CYP3A inhibitors (eg, boceprevir, cobicistat, conivaptan, itraconazole, ketoconazole, and posaconazole, ritonavir alone and with danoprevir or elvitegravir or indinavir or lopinavir or paritaprevir or ombitasvir or dasabuvir or saquinavir or tipranavir, telaprevir, troleandomycin, and voriconazole, grapefruit juice or grapefruit/grapefruit-related citrus fruits [eg, Seville oranges, pomelos]) is not recommended and alternate medications should be considered. If the concomitant use of the strong CYP3A inhibitor cannot be avoided, reduce the starting dose of lorlatinib from 100 mg orally once daily to 75 mg orally once daily. In patients who have had a dose reduction to 75 mg orally once daily due to adverse reactions and who initiate a strong CYP3A inhibitor, reduce the lorlatinib dose to 50 mg orally once daily. If concomitant use of a strong CYP3A inhibitor is discontinued, increase the lorlatinib dose (after 3 plasma half-lives of the strong CYP3A inhibitor) to the dose that was used before starting the strong inhibitor.

- Use of strong CYP3A inducers with lorlatinib is contraindicated. Lorlatinib metabolism may be induced when taking strong CYP3A inducers (eg, carbamazepine, enzalutamide, mitotane, phenytoin, rifampin, St. John's Wort) resulting in reduced plasma concentrations. Furthermore, when lorlatinib was coadministered with rifampin, increases in AST and ALT were noted. Discontinue strong CYP3A inducers for 3 plasma half-lives of the strong CYP3A inducer prior to initiating lorlatinib and until lorlatinib is permanently discontinued. In addition, use with moderate CYP3A inducers (eg, bosentan, efavirenz, etravirine, modafinil) should be avoided due to the potential reduction in lorlatinib exposure.
- Lorlatinib induces CYP2B6 (in vitro) so concurrent use of drugs that are CYP2B6 substrates, such as bupropion and efavirenz, may have less effect. Concomitant CYP2B6 substrates should be used with caution, as the net clinical effect of lorlatinib on CYP2B6 is currently being investigated.
- Lorlatinib induces CYP3A (in vivo) which may lead to a decreased effect of concurrently used CYP3A substrates (eg. hormonal contraceptives etc.). Coadministration of lorlatinib with CYP3A substrates with a narrow therapeutic index (NTI) such as alfentanil, fentanyl (including transdermal patch), astemizole*, cisapride*, cyclosporine, dihydroergotamine, ergotamine, pimozone, quinidine, sirolimus, tacrolimus, terfenadine* (*withdrawn from US market) is not permitted at study entry. However, if it is absolutely necessary to use, sponsor approval is required and the dose of the CYP3A substrate may need to be increased. The NTI CYP3A substrate should be started only after at least 14 days of continuous lorlatinib dosing. If there is a change in the lorlatinib dosing regimen such as a dosing interruption or dose reduction, the administration of the NTI CYP3A substrate should be stopped and resumed at a readjusted dose only after at least 14 days of resumed lorlatinib dosing.
- Lorlatinib inhibits P-glycoprotein (P-gp) (in vitro) so concurrent use of drugs which are P-gp substrates with a narrow therapeutic index (NTI) may have increased effect. The concurrent use of drugs which are NTI P-gp substrates, such as digoxin is not permitted at study entry. The use of these drugs during the study is not recommended and alternate medications should be considered. If absolutely necessary to use during the study, it should be initiated following sponsor approval, and be used then with caution. The net clinical effect of lorlatinib on P-gp is currently being investigated.

Any questions regarding the use of alternative medications should be directed to the sponsor for guidance.

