1.2.3.3.2. Clinical Drug-Drug Interaction

In vitro, lorlatinib is a time-dependent inhibitor as well as an inducer of CYP3A4/5 and activates the human pregnane X receptor (hPXR), with a net induction effect on CYP3A4/5 in vivo. Coadministration of lorlatinib and midazolam (MDZ) in patients resulted in decreased mean oral MDZ (a CYP3A4 substrate) AUC and C_{max} after 25 mg and 150 mg QD lorlatinib dosing, compared with those for MDZ alone. Coadministration of lorlatinib with CYP3A4/5 substrates with narrow therapeutic indices should be avoided.

Coadministration of 200 mg daily doses of itraconazole (a strong CYP3A4/5 inhibitor) with a single 100 mg of lorlatinib increased lorlatinib AUC_{inf} by 42% and C_{max} by 24%. An alternative concomitant medicinal product with less potential to inhibit CYP3A4 should be considered. If a strong CYP3A4/5 inhibitor must be coadministered, a dose reduction of lorlatinib from the starting dose of 100 mg QD to 75 mg QD is recommended.

Coadministration of 600 mg daily doses of rifampin (a strong CYP3A4/5 inducer) with a single 100 mg dose of lorlatinib decreased lorlatinib AUC_{inf} by 85% and C_{max} by 76%. Concomitant administration of lorlatinib and rifampin led to elevated AST and ALT levels in all subjects. Use of strong CYP3A4/5 inducers with lorlatinib is contraindicated. Avoid concomitant use with moderate CYP3A4/5 inducers if possible, as they may also reduce lorlatinib plasma concentrations.

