CNS effects could be categorized into 3 different categories including cognitive effects, mood effects and speech effects, which have been reported separately. The treatment related including cognitive effects, mood effects and speech effects have been observed in 21.7%, 15.3%, 8.1% patients in the 100-mg pooled group of Study 1001. The most common treatment related AEs in each category are memory impairment and irritability, slow speech, each occurring in 9.5%, 5.8% and 3.4% patients.

The CNS effects reported in both Phase 1 and Phase 2 portions have been generally considered mild (Grade 1 and Grade 2) in severity and transient, and improved upon dose delay and/or dose reduction. No Grade 4 or 5 CNS effects have been reported in the Phase 1 or Phase 2 portions. A more detailed evaluation of CNS effects is ongoing in the Phase 2 portion by routine assessment of cognition, mood, and suicidality through a computerized test (using laptops provided by Cogstate). Based on the preliminary results observed, the assessments in this Phase 2 study will be limited to mood and suicidality.

Changes in QTc and PR prolongation have also been observed in the study. QT interval prolongation was reported as treatment related AE in 5.4% patients in the 100-mg pooled group of Study 1001. And no Grade 3, Grade 4, Grade 5 treatment related AE have been reported. There were no atrioventricular block events in Phase 1, Grade 1 atrioventricular block was reported in 2 patients in Phase 2 as treatment related AE. No Grade 2 and above treatment related atrioventricular block have been reported. Basing on the preliminary evidence, the assessment of ECG and heart function will be conducted in this Phase 2 study.

In the 100-mg pooled group of Study 1001, 11.3% patients had a maximum decrease from baseline in LVEF $\geq 20\%$. The mechanism for the LVEF decreases is currently unclear, and it will need be further explored. Thus, the decrease of LVEF will also be evaluated in this study.

Peripheral neuropathy, mood disorders, cognitive disorders, speech disorders, vision disorders, diarrhoea, constipation, arthralgia, oedema, fatigue, weight increased are identified risks associated with lorlatinib administration, for which dose delay and/or dose reduction have been effective.

For complete details of the nonclinical/clinical studies, refer to lorlatinib current investigator's brochure

Efficacy

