5.5. Recommended Dose Modifications

Every effort should be made to administer investigational products on the planned dose and schedule. In the event of significant toxicity, dosing may be delayed and/or reduced as described below. In the event of multiple toxicities, dose modification should be based on the worst toxicity observed. Subjects are to be instructed to notify their investigators at the first occurrence of any adverse event.

If a dosing interruption longer than 4 weeks due to ongoing treatment-related toxicity is necessary, study treatment should be permanently discontinued, unless there is a discussion of the clinical circumstance with the sponsor's medical monitor and agreement that the subject may resume treatment after a lapse of greater than 4 weeks.

In case of adverse events, investigators are encouraged to employ best supportive care according to local institutional clinical practices or follow the guidance for selected adverse events provided in [Table 2](#). Subjects will be monitored closely for toxicity, and the dose of lorlatinib may be adjusted as indicated in [Table 1](#) below. All dose modifications will be reported in the Case Report Form (CRF).

Table 1. Lorlatinib Dose Levels for Inpatient Dose Modifications

Dose Levels	Lorlatinib dose
0	100 mg QD
-1	75 mg QD
-2	50 mg QD

Dose reductions below dose level -2 are not allowed.

Inpatient dose reduction by 1 and, if needed, 2 dose levels will be allowed depending on the type and severity of toxicity encountered (Dose Level -1 is 75 mg QD; Dose Level -2 is 50 mg QD). It is recommended that in case of lorlatinib dose decrease, the subject is assigned new drug rather than using less tablets from the bottle assigned at previous visit.

If a subject has a significant toxicity from lorlatinib treatment which fails to recover within 28 days (4 weeks) or, in the opinion of the investigator, requires permanent discontinuation of the treatment based on the severity of the adverse event, then this subject should not be further treated with lorlatinib but should remain in the study with ongoing tumor assessments until RECIST-defined disease progression by the ICR.

Recommendations for lorlatinib dose modification for treatment-related non-hematological and hematological toxicity, as well as for treatment-related toxicity of special interest, are provided in Table 2 below.

Re-escalation is not allowed except if discussed with and approved by the sponsor’s medical contact.

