CNS effects ^b	Continue lorlatinib at the same dose or withhold dose until recovery to baseline. Then resume at the same dose or reduce by 1 dose level	Withhold dose until toxicity is less than or equal to Grade 1. Then resume at 1 reduced dose level	Withhold dose until toxicity is less than or equal to Grade 1. Then resume at 1 reduced dose level	Permanently discontinue lorlatinib
^b Examples of CNS effects could include changes in speech, memory, sleep, cognition, or vision.				

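### Section 5.9.1's return to the pre-inhibitor dose makes no exception for a toxicity reduction made while the inhibitor was in use

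*Protocol*

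**What the plan says.** Protocol Section 5.9.1 discourages strong CYP3A inhibitors on study: co-administration "is not recommended and alternate medications should be considered". If one is unavoidable, the dose goes from 100 to 75 mg once daily. A second rule covers toxicity that came first: "In patients who have had a dose reduction to 75 mg orally once daily due to adverse reactions" and who then start an inhibitor, the dose goes to 50 mg. When the inhibitor stops, the site is to "increase the lorlatinib dose (after 3 plasma half-lives of the strong CYP3A inhibitor) to the dose that was used before starting the strong inhibitor". No approval step is attached.

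Section 5.5 governs toxicity. Table 1 has three levels (100, 75 and 50 mg), and "Dose reductions below dose level -2 are not allowed". Table 2 calls for one level down for several toxicities. For Grade 2 or 3 CNS effects it reads: "Withhold dose until toxicity is less than or equal to Grade 1. Then resume at 1 reduced dose level". On going back up, Section 5.5 says: "Re-escalation is not allowed except if discussed with and approved by the" sponsor's medical contact. It makes no exception for increases under Section 5.9.1.

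Neither section refers to the other on this point.

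**The concern.** The return instruction fixes its target as the dose before the inhibitor. That is right when the inhibitor was the only reason for the lower dose. It is wrong when a toxicity led to a further reduction while the inhibitor was in use, because the target then removes both reductions.

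The drafting makes this easy to miss. Where Section 5.9.1 wants sponsor approval, it says so, as it does for narrow-therapeutic-index CYP3A and P-gp substrates. It says nothing similar for this increase. Its closing line about sponsor guidance concerns alternative medications only.

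At stake is the safety of an individual patient. A site working from Section 5.9.1 alone would give 100 mg to someone who had needed a toxicity reduction. Section 1.2.3.4 reports that CNS effects "improved upon dose delay and/or dose reduction". Section 1.2.3.3.3 reports that the probability of any Grade 3 or higher treatment-emergent event rose with exposure. For Grade 2 pneumonitis, Table 2 requires resumption one level lower and permanent discontinuation on recurrence, so undoing that reduction could cost the patient the drug.

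**Working it through.** The plan states no figure on this point, so there is none to reproduce. The check traces the dose paths and then scales the result.

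**Inputs**
- Dose levels 100, 75 and 50 mg, with no lower level: Section 5.5, Table 1.
- Inhibitor steps 100 to 75 mg and 75 to 50 mg, and the return rule: Section 5.9.1.
- Effect of itraconazole on a single 100 mg lorlatinib dose: AUCinf up 42% (ratio 1.42), Cmax up 24% (ratio 1.24): Section 1.2.3.3.2.
- Assumptions: dose proportionality, and the single-dose ratios apply during continuous dosing.

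**Step 1: paths**

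| Path | Dose under the 5.9.1 return rule | Toxicity reduction kept? |
|---|---|---|
| 100 → 75 (inhibitor) → inhibitor stopped | 100 mg | none was made |
| 100 → 75 (inhibitor) → 50 (toxicity) → inhibitor stopped | 100 mg | no |
| 100 → 75 (toxicity) → 50 (inhibitor) → inhibitor stopped | 75 mg | yes |

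Because 50 mg is the floor, the second path is the only one on which a toxicity reduction can fall during inhibitor use. The second and third paths contain the same two reductions and differ only in their order. On the second path, Section 5.5 leaves the patient at 50 mg unless the sponsor approves an increase. Neither section names 75 mg, the dose that reverses only the interaction step.

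**Step 2: exposure at which the toxicity arose** (75 mg with inhibitor, in mg-equivalents of lorlatinib alone)
- AUC: 75 × 1.42 = 106.5
- Cmax: 75 × 1.24 = 93.0

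**Step 3: exposure after the inhibitor stops, relative to step 2**

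| Dose alone | AUC | Cmax |
|---|---|---|
| 100 mg | 100/106.5 = 94% | 100/93.0 = 108% |
| 75 mg | 75/106.5 = 70% | 75/93.0 = 81% |

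For comparison, an ordinary one-level reduction leaves 75/100 = 75% or 50/75 = 67% of the exposure at which a toxicity arose. The third path ends at 75/100 = 75%. By AUC, 75 mg sits inside that 67% to 75% range. By Cmax it sits somewhat above it. For 100 mg to be as low as 75%, the inhibitor ratio would have to be 100/(75 × 0.75) = 1.78, above both documented values.

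**Step 4: change from the reduced dose the patient was taking** (50 mg with inhibitor)
- AUC reference: 50 × 1.42 = 71.0. Moving to 100 mg alone gives 100/71.0 = 1.41 times this; moving to 75 mg gives 75/71.0 = 1.06 times.
- Cmax reference: 50 × 1.24 = 62.0. Moving to 75 mg alone gives 75/62.0 = 1.21 times this.

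So even 75 mg is an increase over the reduced exposure: about 6% by AUC and 21% by peak. This bears on how the fix is worded.

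**The case against.** The strongest reply is that existing text already catches this path. Section 5.5's bar on re-escalation is unqualified and sits in the section on toxicity dosing. A patient cut to 50 mg for toxicity falls within it. Both sections can be obeyed at once: Section 5.9.1 gives a target and Section 5.5 adds an approval step. This stands. A reader might infer that the two sections contradict each other, or that patients are unguarded. The documents do not support that, because a site that reads both would contact the sponsor. What remains is that the stated target is wrong for this patient, and that reading Section 5.5 literally would also require approval for the routine 75 to 100 mg return, which Section 5.9.1 does not mention.

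The harm is also unproven, and this too stands. A reader might infer that 100 mg is shown to be unsafe for such a patient. Section 1.2.3.4 describes 100 mg once daily as well tolerated in Phase 1, and the CNS effects found intolerable by some patients were at 150 and 200 mg once daily. No exposure-response for CNS effects between 75 and 100 mg is given. For general Grade 3 non-hematologic and Grade 3 or 4 hematologic toxicity, Table 2 permits rechallenge at the same dose, so a return to near the original exposure is not in itself contrary to the protocol. The point therefore concerns toxicities for which the dose was actually reduced under Table 2.

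The percentages are also soft. They rest on one inhibitor and a single lorlatinib dose, and Section 1.2.3.3.2 reports net CYP3A induction by lorlatinib in vivo, so steady-state ratios may differ in either direction. AUC and Cmax fall on opposite sides of 100%. The gap in the text does not depend on these figures.

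**Conclusion.** The point holds as a minor dosing-safety correction. On one path, Section 5.9.1 names a dose that reverses a toxicity reduction, while the same two reductions in the other order leave the patient at 75 mg. On the documented single-dose ratios, with dose proportionality assumed, 100 mg returns the patient to about 94% (AUC) or 108% (Cmax) of the exposure at which the toxicity arose, against 70% or 81% at 75 mg.

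The documents give no frequency for this path, and none is claimed. Rarity is an inference: exclusion criterion 15 bars strong CYP3A inhibitors within 12 days before the first dose, and they are discouraged on study. The textual gap is certain; the size of its consequence is not. A reader might also infer some effect on the trial's results. There is no basis for that: the ORR test and the sample size do not depend on this rule.

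**What to change.** Add to Section 5.9.1: *If the dose was reduced for toxicity during inhibitor use, do not return automatically to the pre-inhibitor dose. Any increase needs sponsor approval under Section 5.5 and should not exceed the pre-inhibitor dose less the level(s) removed for toxicity (75 mg for a patient who went 100 to 75 to 50 mg) unless the sponsor specifically agrees.*

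Add to Section 5.5: *Reversing a purely interaction-driven reduction under Section 5.9.1 is not re-escalation.*

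The first addition keeps the sponsor step even for the move to 75 mg. An automatic move to 75 mg would be looser than Section 5.5 now is and, from step 4, would raise the peak by about 21% in a patient with recent toxicity. The second addition frees routine returns from an approval step that Section 5.9.1 does not mention.

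The cost is a few sentences in a clarification letter or the next amendment, with no new procedures, data or patients. The downside is that some patients may stay at 50 mg until the sponsor has been consulted.
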